## 6 TRIAL DESIGN

Our trial will be designed as a cluster randomised controlled trial and powered as a superiority trial for our primary outcome. **For the secondary outcome, the trial will seek to establish non-inferiority. The trial will have sufficient statistical power for both outcomes and will include of a three month intervention period and a six month follow-up period.**

**Six months after the end of the intervention period**, all participants will receive our intervention and we will continue to measure appropriateness and volume of testing in a prospective observational design in the original intervention group as a measure of sustainability.

We will randomize participating PCPs to the intervention or to a control group. The unit of allocation is the PCP. This means that all physicians in the same practice will be allocated to the same intervention and that either all or no physicians in the PCP will be included in the trial. All patients cared for by the same primary care practice will be exposed to the same intervention. In this description, we assume the recruitment of 300 physicians. In the case where less physicians are recruited, we will use an adaptive design as described in [Appendix 3](#).

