To our knowledge there are no sound statistics on the percentage missed diagnoses due to laboratory testing in primary care. Panesar et al (Panesar 2016) estimated that two to three per hundred consultations in primary care result in safety incidents. Between 4 and 45% of these safety incidents may be related to misdiagnosis or missed diagnoses. Assuming 2.5% missed diagnoses in primary care, we calculated that the trial, with an 80% power to detect a non-inferiority of a 1% difference using a significance level of 5%, would need 6032 patients in total. Previous studies have illustrated that in primary care ICCs for clinical outcomes are lower than those for process outcomes and the ICC for adverse effects to be around 0.025 (Adams 2004). Although this may not seem correct, the chances that a physician consistently misses the same diagnosis is less probable than consistently ordering the same test for the same indication. A missed or delayed diagnosis will more probably lead to a change in practice than over- or underutilization of a laboratory test. For this outcome, the unit of analysis will be individual patients and not individual tests as for appropriateness. Therefore, there is one level of clustering less to account for. Assuming a 3 month period in which laboratory tests are ordered for 42 patients, we would need to recruit 290 physicians. In the case of a 6 month period, implying 84 patients for which a laboratory panel is requested, we would need to recruit 220 physicians. For this clinical outcome we will not account for clustering on the level of the PCP as there is no evidence that this influences the amount missed diagnoses by individual physicians. Intuitively, there is no reason to assume that two physicians working together in the same practice would have a greater probability of missing the same diagnosis. Because we believe this outcome to be important in convincing physicians in the widespread use of order sets for laboratory tests, we have chosen to power our study to include this outcome. Figure 16 summarises all the sample size calculations for the outcome 'missed or delayed diagnoses' and their assumptions.

Sample size for comparison of 2 proportions (binary values): non-inferiority trial  
 Missed diagnoses: pA: 2.5%  
 Missed diagnoses: pA: 2.5%  
 Clinically significant change of 1%  
 $\alpha = 0.05$   
 $1-\beta = 0.80$   
 $K = 1$   
 Sample size: 6032  

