### 9.1.3 Final sample size

The trial will have sufficient power for both the primary and secondary outcome. Hence, a total of 300 physicians will be included.

Therefore the trial will be overpowered for the primary endpoint and be able to detect much smaller differences between the two groups than the predefined difference of 10% that was set out to be found. Therefore, assuming a sample of 300 recruited physicians, the minimal difference that can be found with a statistical power of 90% using a significance level of 5%, based on the assumptions described in section 9.1, was calculated. With 300 recruited physicians, it is expected that the trial will include 12600 patients and a total of 63000 tests. Removing the design effect (by dividing by 12.465), this corresponds with a total of 5054 'independent' tests and provides the trial with a 90% power to detect a difference as small as 4.1%.

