## 1.1 Sample size calculations

Sample size for comparison of 2 proportions (binary values): non-inferiority trial  
Missed diagnoses: pA: 2.5%  
Missed diagnoses: pA: 2.5%  
Clinically significant change of 1%  
 $\alpha = 0.05$   
 $1-\beta = 0.80$   
 $K = 1$   
Sample size: 6032  
Sealed Envelope Ltd. 2012. Power calculator for binary outcome non-inferiority trial. [Online] Available from: <https://www.sealedenvelope.com/power/binary-noninferior/> [Accessed Wed Jul 20 2016].  
 $DE = 1 + \rho(n-1)$   
 $n$  = number individuals per cluster  
 $\rho$  = intraclass correlation coefficient  
We account only for the clustering on the level of the physician.  
 $n = 42$  for a trial lasting 3 months  
 $n = 84$  for a trial lasting 6 months  
 $\rho = 0.025$   
for a trial lasting 3 months:  $DE = 2.025$  which implies **290 physicians ( $\approx 300$  physicians)**  
for a trial lasting 6 months:  $DE = 3.075$  which implies **220 physicians**

**Figure 1:** Sample size calculations for secondary outcomes missed or delayed diagnoses including inflation due to clustering

[figure not shown]

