3.3. Sample size

For sample size calculations, we refer to the protocol and appendix 3 of the protocol. At the end of the six-month intervention period the planned sample size was verified based on the number of recruited physicians and the average number of patients per physician. With 280 study physicians (clusters), a sample of 12740 patients (45.5 patients on average per physician) would be necessary to have at least 80% power for the secondary outcome (diagnostic error), assuming the original intra-cluster correlation and diagnostic error rates. At that point we had recruited 11200 patients and it was deemed unfeasible to recruit an additional 1500 patients. Since most recruitments were realised by physicians who had already recruited 50 or more patients, the Steering Committee agreed that attempts to recruit additional patients should target physicians with a low number of recruited patients. Therefore, only those physicians who had not yet recruited 10 patients were allowed another month to recruit additional patients. Specific calculations regarding the sample size and the assumed intra-cluster correlations can be found in the protocol under 9.1.

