10.2.2. Secondary outcome analysis

Diagnostic error

The proportion of patients with a missed diagnosis will be analysed by means of a logistic GEE model that includes allocated group and laboratory as factors and uses PCP as the clustering variable. An independent working correlation matrix will be used. The proportion of patients with a missed diagnosis and associated 95% confidence intervals will be estimated from the model.

The difference in proportions will be obtained by subtracting the two proportions. The associated standard error will be calculated from the rules for the variance of a difference between two independent estimates. The 95% confidence interval for the difference will be calculated.

The non-inferiority limit for missed diagnoses is 1%, i.e. the intervention will be deemed non-inferior if the difference between the allocated groups (intervention – control) is less than 1%. Therefore, the intervention will be deemed non-inferior if the upper limit of the 95% confidence interval lies below 1.

As for the primary endpoint, the analysis will be performed for all 17 study indications together. An additional analysis will be performed that only includes patients who have no indications in addition to the 17 study indications

Test volume

The total number of tests will be analysed using a GEE model for count data (Poisson or Negative Binomial to handle potential overdispersion) that includes allocated group and laboratory as factors in the model and PCP as clustering variable. No offset will be used. The number of tests per patient for each group will be estimated from the model and presented together with their associated 95%

confidence intervals. The effect of the intervention will be presented as the ratio between the two numbers with its 95% confidence interval. Statistical significance will be assessed at a significance level of 5%.

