10.3. Missing data

For about 15% of patients included in the study, no eForm is available (preliminary figures). This measure of missing data is due to technical difficulties in the pseudonymized data collection. No methods for data imputation are foreseen. Patients for whom no data was collected will be excluded from the data analysis. The exact measure of missing data will be reported in the final report.

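### The non-inferiority sample size of 6032 gives 80% power only for a one-sided 5% test; under the stated 95% confidence interval rule it gives about 70%

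*Protocol*

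**What the plan says.** Protocol 9.1.2 assumes 2.5% missed diagnoses in both arms and a margin of 1 percentage point, and gives the sample size in these words: "with an 80% power to detect a non-inferiority of a 1% difference using a significance level of 5%, would need 6032 patients in total". Figure 16 and Appendix 3, section 1.1, repeat the inputs (alpha 0.05, power 0.80, 1:1 allocation) and the result, "Sample size: 6032". None of these places gives the sidedness of alpha. With an ICC of 0.025 at physician level, the figure becomes 290 physicians (rounded to 300) at 42 patients each, or 220 at 84 each.

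The decision rule is the same in Protocol 9.3.3.1 and SAP 10.2.2: "the intervention will be deemed non-inferior if the upper limit of the 95% confidence interval lies below 1". Neither document mentions a one-sided limit or a 90% interval.

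SAP 3.3 rechecks the size with 280 physicians and finds that "a sample of 12740 patients (45.5 patients on average per physician) would be necessary to have at least 80% power", under the original ICC and error rate. It continues: "At that point we had recruited 11200 patients and it was deemed unfeasible to recruit an additional 1500 patients".

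Protocol 9.1.3 concludes: "The trial will have sufficient power for both the primary and secondary outcome". Protocol 6 says the same ("The trial will have sufficient statistical power for both outcomes"), and SAP 3.1 repeats it.

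**The concern.** The sample size and the decision rule appear to use different significance levels. If non-inferiority is read from the upper limit of a two-sided 95% interval, the test is one-sided at 2.5% and needs more patients than a one-sided 5% test for the same power.

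This matters because the outcome, although secondary, determined the size of the trial: 290 to 300 physicians, against 35 for appropriateness (Figures 15 and 16). Protocol 9.1.2 explains that the trial was powered for it because the result is meant to persuade physicians that order sets are safe to use. If real power is near 70%, the chance of failing to show non-inferiority when there is truly no difference is about 30%, not the planned 20%. An inconclusive result would then be judged against a power the trial did not have. If the interval is left undefined, its sidedness could also be settled after the data are seen.

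**Working it through.** **Inputs** (Protocol 9.1.2 and Figure 16 unless noted): p = 0.025 in both arms, true difference 0, margin d = 0.01, power 0.80, 1:1 allocation, physician ICC 0.025. SAP 3.3 supplies 280 physicians, 12,740 patients (45.5 each) and 11,200 recruited (40 each).

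**1. Reproduce 6032.** n per arm = (z_alpha + z_0.80)² × 2p(1 − p) / d²
- One-sided 5%: (1.645 + 0.842)² × 2 × 0.025 × 0.975 / 0.01² = 3014.0 per arm, total 6028. This matches 6032 to within 0.1%.
- One-sided 2.5%: (1.960 + 0.842)² × 2 × 0.025 × 0.975 / 0.01² = 3826.3, rounded up to 3827 per arm, total 7654. This does not match.

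**2. Power of the stated rule at 6032.** SE = √(2 × 0.025 × 0.975 / 3016) = 0.00402, so d/SE = 2.487.
- One-sided 5%: Φ(2.487 − 1.645) = 80.0%
- Upper limit of a two-sided 95% interval: Φ(2.487 − 1.960) = 70.1%

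A simulation of 400,000 trials with Wald intervals and independent patients gave 80.1% and 70.2%.

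**3. Carry it through the clustering.** With K physicians and m patients each, effective N = K × m / (1 + 0.025(m − 1)), and power = Φ(0.01/SE − z_alpha) with SE = √(2 × 0.025 × 0.975 / (N_eff/2)).

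| Scenario | Effective N | One-sided 5% | 95% CI rule |
|---|---|---|---|
| 300 × 42 | 6222 | 81.1% | 71.4% |
| 220 × 84 | 6010 | 79.9% | 69.9% |
| 280 × 45.5 (12,740) | 6031 | 80.0% | 70.1% |
| 280 × 40 (11,200) | 5671 | 77.8% | 67.4% |
| 280 × 34 (11,200 less 15%) | 5216 | 74.8% | 63.8% |

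The last row takes the figure in SAP 10.3 ("For about 15% of patients included in the study, no eForm is available (preliminary figures") and assumes that the loss is even across physicians.

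**4. The SAP recheck uses the same base.** Solving N = B × (1 + 0.025(N/280 − 1)) gives N = 12,727 for B = 6028 and 12,746 for B = 6032. These bracket the SAP's 12,740. With B = 7654, the same equation gives about 23,570 patients. Against 11,200 recruited, the shortfall is then about 12,400 rather than about 1500.

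**5. Size for 80% power under the 95% CI rule.**
- 42 patients each: 7654 × 2.025 / 42 = 369.03, so 370 physicians (stated: 290)
- 84 patients each: 7654 × 3.075 / 84 = 280.2, so 281 physicians (stated: 220)

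**6. Sensitivity to the event rate, 95% CI rule.**

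| Rate in both arms | 300 × 42 | 11,200 patients |
|---|---|---|
| 2.5% (planned) | 71.4% | 67.4% |
| 2.0% | 80.4% | 76.7% |
| 1.35% | 92.8% | 90.4% |

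**The case against.** **A one-sided 95% limit may have been meant.** The hypothesis runs in one direction, the documents never call the interval two-sided, and 6032 is then exactly right. This cannot be excluded, and the 70% figure depends on the two-sided reading. That reading is the more natural one: the same paragraphs give 95% intervals for each arm's proportion, and nothing marks the interval for the difference as a different kind. If one-sided was meant, the rule still has to say so.

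**The planning rate is high relative to the documents' own sources.** Protocol 3.3.2.1 cites a range from below 0.1% to 2.5%. The figures in 9.1.2 (2 to 3 incidents per 100 consultations, 4 to 45% of them diagnostic) imply 0.08% to 1.35%. At 1.35% power exceeds 90% even under the stricter rule. This is a fair point about the likely consequence. It does not rescue the stated claim, which is 80% at 2.5%, and SAP 3.3 explicitly keeps that rate.

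**The corrected figures are themselves approximate.** They assume equal clusters, yet SAP 3.3 describes physicians with 50 or more patients alongside others with fewer than 10. With an assumed coefficient of variation of cluster size of 0.5 or 0.7, the design effect 1 + 0.025((1 + CV²) × 40 − 1) is 2.225 or 2.465, and power at 11,200 falls to about 62% or 58%. They also ignore clustering by practice, on which the analysis is based. Nor is 11,200 the final count, since SAP 3.3 and 6.3.1 describe later additions and exclusions. The corrected figures therefore need these caveats beside them. Uneven clusters and practice-level correlation would lower power further; neither restores 80%.

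**The recruitment shortfall and the missing eForms are separate, disclosed matters.** That is correct. The mismatch alone accounts for the drop from 80% to about 70%; the 67% and 64% figures add those two effects.

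**Conclusion.** The concern holds. The figure 6032 is correct arithmetic for a one-sided 5% test; the fault is that it does not belong to the decision rule in Protocol 9.3.3.1 and SAP 10.2.2. At the plan's own inputs that rule has about 70% power at the planned size, roughly 10 points below the claim, and reaching 80% would take 27% more effective patients (7654/6028 = 1.27). The conclusion rests on reading the interval as two-sided and on a 2.5% rate with no true difference. The clustered figures also rest on the protocol's physician-level ICC of 0.025 and equal cluster sizes. The mismatch is conservative for type I error: a positive non-inferiority finding would not be weakened by it. What is wrong is the stated power, and with it how an inconclusive result would be interpreted.

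**What to change.** Keep the 95% interval rule and the planned size, and correct the power statements.

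- **Protocol 9.1.2, Figure 16 and Appendix 3:** state that 6032 effective patients give about 70% power under the rule (about 71% for 300 × 42, about 70% for 220 × 84), and that 80% would need 7654 effective patients, about 370 physicians at 42 each.
- **SAP 3.3:** state that 12,740 patients give about 70% and the 11,200 recruited about 67%, before missing eForms, assuming equal clusters and physician-level clustering only.
- **Protocol 6, Protocol 9.1.3 and SAP 3.1:** qualify the claim of sufficient power for this outcome.
- **Protocol 9.3.3.1 and SAP 10.2.2:** say that the interval is two-sided, and write the threshold as 1 percentage point (0.01).

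Only if a one-sided 5% test was the original intention, state instead, before unblinding, that non-inferiority is read from the two-sided 90% interval (the one-sided 95% limit). The figures 6032 and 80% then stand for the planned size, although 11,200 patients would still give 77.8%. Moving to that interval for any other reason would relax the rule after a known shortfall.

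The cost is wording in the protocol and SAP and a less favourable stated power. No extra patients are needed, and the main option leaves the decision rule unchanged.

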### 9.1.3 Final sample size

The trial will have sufficient power for both the primary and secondary outcome. Hence, a total of 300 physicians will be included.

Therefore the trial will be overpowered for the primary endpoint and be able to detect much smaller differences between the two groups than the predefined difference of 10% that was set out to be found. Therefore, assuming a sample of 300 recruited physicians, the minimal difference that can be found with a statistical power of 90% using a significance level of 5%, based on the assumptions described in section 9.1, was calculated. With 300 recruited physicians, it is expected that the trial will include 12600 patients and a total of 63000 tests. Removing the design effect (by dividing by 12.465), this corresponds with a total of 5054 'independent' tests and provides the trial with a 90% power to detect a difference as small as 4.1%.

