Figures and statistics on appropriateness of laboratory testing are grossly lacking, due to heterogeneity in the definition of appropriateness and differences in appropriateness criteria depending on the type of test. A robust figure, that seems reiterated in various studies, is that the proportion inappropriate laboratory tests is found to be around 30% (Zhi 2013, van Walraven 1998). It is believed that when using order sets in a CPOE, the appropriateness of laboratory ordering will improve. We propose that the trial should have 80% power to detect a 10% difference (in this case, from 30% to 20%) using a significance level of 5%. Appropriateness will be measured as the proportion of inappropriate study tests recorded through the CPOE. The unit of randomization is the PCP and not the patient or test, hence it is necessary to account for the lack of independence between the various tests, patients treated by the same physician and physicians working in the same PCP. In our design we account for clustering on multiple levels; clustering on the level of the individual tests ordered for the same patient, clustering for ordering patterns of the same physician for different patients and clustering for ordering patterns of physicians practicing within the same PCP. Estimates of intraclass correlation coefficients (ICCs) for process of care measures in primary care are between 0.05 and 0.15 (Campbell 1999, Campbell 2000), however estimates for ICCs regarding appropriateness of laboratory tests have been shown to vary between 0.04 and 0.288 (Littenberg 2006). To our knowledge no ICCs have been published for clustering on the various levels observed in our trial, therefore we have chosen to use a very conservative ICC estimate of 0.2 for each level of clustering in our sample size calculations, probably overestimating the design effect. Using methods proposed by Campbell (Campbell 2004) we would need 586 tests over both arms if unadjusted for clustering. We hypothesize that each panel will include approximately 5 study tests and that physicians will order laboratory tests for 42 patients per 3 months using the CPOE, assuming a 70% usage of the CPOE (van Wijk 2001). To account for clustering on the PCP level, we assume 2.35 physicians per PCP based on preliminary data from an ongoing trial (Heselmans 2013). In this situation the amount of tests would be inflated to 7305 tests, or 35 physicians in a trial lasting 3 months, taking into account multi-level clustering and attenuation of the clustering due to the amount of measures per patient (Teerenstra 2008). Figure 15 summarises the sample size calculations for the outcome appropriateness and their assumptions.

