
Sample size for comparison of 2 proportions (binary values): 2-sided equality

Appropriateness: pA: 70%

Clinically significant change of 10% (to pB: 80%)

$\alpha = 0.05$

$1-\beta = 0.80$

$K = 1$

Sample size: 586

Sample size calculations based on Campbell et al (Campbell 2004) for a trial with 80% power to detect a difference of 10% (increase of appropriateness from 70% to 80%) with a significance of 10% predict 586 tests.

Design effect of clustering on sample size based on Teerenstra et al (Teerenstra 2008):

4 level setting comprising test, patient, physician and primary care practice:

1. Multiple study tests per patient, assumed to be 5 per patient,
2. Multiple patients per physicians, assumed to be 42 per 3 months if there is 70% use of the online intervention and 1/3 indications included in the study,
3. Multiple physicians per primary care practice (PCP), assumed to be 2.35 based on preliminary data by Heselmans et al. (Heselmans 2013)

We assume an intracluster coefficient of 0.2 for each level of clustering.

$Rho_n$  = correlation between two physicians active in the same PCP

$Rho_s$  = correlation between two patients cared for by the same physician

$Rho_e$  = correlation between two tests ordered for the same patient

$n_n$  = mean amount of physicians per PCP

$n_s$  = mean amount of patients per physician

$n_e$  = mean amount of study tests per patient

$Phi_e = 1 + Rho_e * (n_e - 1)$

$Phi_s = 1 + Rho_s * (n_s - 1) * w_e$

$Phi_n = 1 + Rho_n * (n_n - 1) * w_n$

$w_e = (n_e * Rho_e) / (1 + Rho_e * (n_e - 1))$

$w_s = (n_s * Rho_s) / (1 + Rho_s * (n_s - 1))$

The final design effect (DE) =  $Phi_e * Phi_s * Phi_n$

Applied to our protocol:

$n_n$  = mean amount of physicians per PCP = 2.35

$n_s$  = mean amount of patients per physician = 42 per 3 months

$n_e$  = mean amount of study tests per patient = 5

$Phi_e = 1 + Rho_e * (n_e - 1) = 1.8$

$Phi_s = 1 + Rho_s * (n_s - 1) * w_e = 5.56$

$Phi_n = 1 + Rho_n * (n_n - 1) * w_n = 1.25$

$w_e = (n_e * Rho_e) / (1 + Rho_e * (n_e - 1)) = 0.56$

$w_s = (n_s * Rho_s) / (1 + Rho_s * (n_s - 1)) = 0.913$

The final design effect (DE) =  $Phi_e * Phi_s * Phi_n = 1.8 * 5.56 * 1.25 = 12.465$

586 test \* 12.465 (DE) = 7305 test = 1460 patients = 35 physicians during 3 months

Figure 15: Sample size calculations for primary outcome appropriateness including inflation due to multi-level clustering

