3.2. Randomisation

Participating PCPs were randomised to the intervention or to the control group. The unit of allocation is the PCP. This means that all physicians in the same practice were allocated to the same intervention and that either all or no physicians in the PCP were included in the trial. All patients cared for by the same primary care practice were exposed to the same intervention. We recruited 288 physicians on 01/12/2017 of which 8 physicians dropped out before including patients. The 280 physicians were distributed across 72 PCPs. We stratified the randomisation according to the laboratory with which they collaborated (3 strata). The level of confidence in using a CPOE was associated with the laboratory with which the PCP collaborated. This also assured that all PCPs collaborating with a laboratory were evenly distributed across both arms. Randomisation was done using a random numbers generator by the trial chief statistician. The research team will remain blinded to the allocation until after database lock. Further details on the randomisation scheme can be found in the protocol under 8.3.

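### The stated 90% power for a 4.1-point difference holds for the planned practices; with the 72 practices reported it is about 81%, and the 90%-power detectable difference is 4.7 points

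*Protocol*

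**What the plan says.** Protocol 9.1.3 notes that the sample is driven by diagnostic error, so the primary endpoint has power to spare. It then works out "the minimal difference that can be found with a statistical power of 90% using a significance level of 5" per cent. For 300 physicians, "it is expected that the trial will include 12600 patients and a total of 63000 tests"; dividing by 12.465 leaves 5054 independent tests, which "provides the trial with a 90% power to detect a difference as small as 4.1" points.

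The 12.465 comes from Protocol 9.1.1, which uses 5 tests per patient, 42 patients per physician, 2.35 physicians per practice and a correlation of 0.2 at each of three levels. The protocol calls this a "very conservative ICC estimate of 0.2 for each level of clustering in our sample size calculations, probably overestimating the design effect". The same section quotes 0.05 to 0.15 for process-of-care measures, and adds that "estimates for ICCs regarding appropriateness of laboratory tests have been shown to vary between 0.04 and 0.288". Protocol section 4 expects about 124 practices.

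SAP 3.2 gives the realised structure: "The 280 physicians were distributed across 72 PCPs". SAP 3.3 re-verifies the sample size for diagnostic error only, with physicians as the clusters, and refers back to the protocol for the rest. SAP 10.2.1 analyses the primary outcome with practice as the clustering variable.

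**The concern.** The 4.1-point figure depends on how physicians are spread over practices, because the practice is the unit of randomisation. About 124 to 128 practices were assumed and 72 are reported, so each holds 3.89 physicians instead of 2.35. More of the sample then shares a practice, the design effect rises and the effective sample falls. No document updates the figure for the primary endpoint.

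A second doubt concerns the label conservative. The three values of 0.2 are not three separate practice-type ICCs. They are nested and attenuated by weights, so the correlation left at practice level is much smaller than 0.2.

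At stake is how the planned precision is described. Protocol 9.1.3 presents the trial as able to detect differences far below 10 points, with a specific figure that the realised design does not reach.

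**Working it through.** **Inputs.** Two-sided 5% ("Sample size for comparison of 2 proportions (binary values): 2-sided equality"), equal arms and control proportion 70% ("Appropriateness: pA: 70" per cent), all from Protocol 9.1.1. Planned structure from Protocol 9.1.1 and 9.1.3. Realised structure from SAP 3.2 and 3.3: 280 physicians, 72 practices, 280/72 = 3.89 physicians per practice, 11,200 patients, 11,200/280 = 40 per physician. Five tests per patient is kept as the protocol's assumption, giving 56,000 tests.

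**Formulas.** Design effect = Φe × Φs × Φn, with Φe = 1 + 0.2(ne − 1), Φs = 1 + 0.2(ns − 1)we, Φn = 1 + 0.2(nn − 1)ws, we = 0.2ne/Φe and ws = 0.2ns/(1 + 0.2(ns − 1)). Power = Φ{[d√n − 1.96√(2p̄(1 − p̄))] / √(p1(1 − p1) + p2(1 − p2))}, with n effective tests per arm.

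**Step 1: the plan's figure reproduces.** Φe = 1.8, we = 0.556, Φs = 5.556, ws = 0.913, Φn = 1.2465; product 12.465. 63,000/12.465 = 5054, or 2527 per arm. For 70% v 74.1%: (2.061 − 1.244)/0.634 = 1.289, so power is 90.1%. The 90%-power detectable difference is 4.09 points.

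**Step 2: realised structure, same correlations.** Φs = 5.333, ws = 0.909, Φn = 1 + 0.2 × 2.889 × 0.909 = 1.525. Design effect = 1.8 × 5.333 × 1.525 = 14.64. 56,000/14.64 gives about 3825 effective tests, or 1912 per arm. For 4.1 points: (1.793 − 1.244)/0.634 = 0.866, so power is 81%. The 90%-power detectable difference is 4.7 points.

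Most of the change comes from the practice count. With 280 physicians and 40 patients each but still 2.35 per practice, the design effect would be 11.96, power 88% and the detectable difference 4.2 points. If 14.3 tests per patient is assumed instead of 5 (close to the panel sizes in Protocol section 4), the realised design gives 83% and 4.6 points.

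**Step 3: what 0.2 at each level implies.** On the single-test scale the same design effect is 1 + (ne − 1)r1 + ne(ns − 1)r2 + ne·ns(nn − 1)r3. This gives:

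- r1 = 0.20, two tests of one patient
- r2 = (10.0 − 1.8)/(5 × 41) = 0.04, two patients of one physician
- r3 = (12.465 − 10.0)/(5 × 42 × 1.35) = 0.0087, two physicians of one practice

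Averaged over all pairs of tests in a practice: (12.465 − 1)/(493.5 − 1) = 0.023.

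SAP 10.2.1 defines the outcome as a per-patient ratio. A mean of 5 tests has 1.8/5 = 0.36 of the variance of one test, so the correlations become 0.04/0.36 = 0.111 within physician and 0.0087/0.36 = 0.024 between physicians of one practice. The average within a practice of 42 × 2.35 = 98.7 patients is (12.465/1.8 − 1)/(98.7 − 1) = 0.061.

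**Step 4: sensitivity with 72 practices.** Single-test scale: design effect = 1 + (56,000/72 − 1) × ICC. Per-patient scale: design effect = 1.8 × [1 + (11,200/72 − 1) × ICC].

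| Within-practice ICC | Scale | Design effect | Power, 4.1 points | Detectable at 90% | Power, 70% v 80% |
|---|---|---|---|---|---|
| 0.04 | patient | 12.9 | 85% | 4.4 | >99% |
| 0.05 | patient | 15.7 | 78% | 4.8 | >99% |
| 0.10 | patient | 29.6 | 51% | 6.6 | >99% |
| 0.15 | patient | 43.5 | 37% | 7.9 | 99% |
| 0.288 | patient | 81.9 | 22% | 10.7 | 86% |
| 0.04 | test | 32.1 | 48% | 6.8 | >99% |
| 0.05 | test | 39.8 | 40% | 7.6 | 99% |
| 0.10 | test | 78.7 | 23% | 10.5 | 87% |
| 0.15 | test | 117.5 | 17% | 12.6 | 71% |
| 0.288 | test | 224.7 | 11% | 16.8 | 45% |

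**The case against.** The strongest reply is that nothing was miscalculated. Protocol 9.1.3 makes the figure conditional on 300 physicians and the section 9.1 assumptions, and on those it is right. The number of practices became known only after recruitment. This stands: the point is an outdated planning value, not an arithmetic error.

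The second reply concerns scale. A reader might infer from 0.009 that the plan used a practice ICC below every value it quotes. The documents do not support that as a general statement. The 0.009 is one component, on the single-test scale, beside 0.20 and 0.04, and Protocol 9.1.1 does not say on which scale its quoted ICCs were estimated. On the per-patient scale of the SAP outcome, the average of 0.061 lies inside both quoted ranges and the within-physician value of 0.111 is well inside them. With the planned practices, a per-patient ICC of 0.04 to 0.05 would even give 97% to 94% power for 4.1 points.

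The single-test figures can also be challenged as extreme. A test-level ICC of 0.15 corresponds to 0.15/0.36 = 0.42 per patient, above the largest quoted value of 0.288. They belong in a range labelled by scale and should not stand alone.

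Finally, a reader might fear that a null result will be taken to exclude differences above 4 points. The SAP reports a 95% confidence interval from a model clustered on practice. That interval, not the planning figure, shows what is excluded.

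What survives is the practice count, which needs no view on ICC scale, and the lack of support for the label conservative.

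**Conclusion.** The point holds in limited form. With 72 practices and the protocol's own correlations, power for 4.1 points is about 81% instead of 90%, and the detectable difference at 90% power is 4.7 points instead of 4.1.

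The claim that the design effect is probably overestimated is unsupported. The implied average within-practice ICC is 0.061 per patient, near the lower end of the quoted ranges, or 0.023 per test, below them. With 72 practices, every quoted process or appropriateness ICC, on either scale, gives less than 90% power for 4.1 points; the best case is 85%.

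A reader might also infer that the 10-point target is underpowered. That is not shown. Its power exceeds 99% under the protocol's correlations, and on the per-patient scale it is 99% at 0.15 and 86% at 0.288. It falls below 80% only on the single-test scale, somewhere between 0.10 (87%) and 0.15 (71%).

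Assumptions: 5 tests per patient, 40 patients per physician and equal cluster sizes. SAP 3.3 shows that recruitment was uneven, which would lower power further. The 72 practices are those of the 280 physicians who remained after 8 dropped out, so the number randomised may be slightly higher.

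**What to change.** Wording only; no extra patients and no change to the analysis.

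1. In SAP 3.3, state that for 280 physicians in 72 practices the primary endpoint has a 90%-power detectable difference of 4.7 points under the protocol's correlations (about 81% power for 4.1). Leave the 4.1 in Protocol 9.1.3 identified as the planning value for 300 physicians at 2.35 per practice.
2. Beside it, give a sensitivity range labelled by scale, since the protocol does not state the scale of its ICCs. For a within-practice ICC of 0.05 to 0.15, this is about 4.8 to 7.9 points if per patient and 7.6 to 12.6 points if per single test. Add that power for the 10-point target stays above 80% except at a single-test ICC near 0.15 or higher.
3. In Protocol 9.1.1, withdraw the two phrases that call the ICC conservative and the design effect overestimated. State instead the implied correlations with their scale: 0.20 / 0.04 / 0.009 between single tests (same patient / same physician / same practice), or an average of about 0.061 within a practice for the per-patient proportion.

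The cost is a less favourable stated figure.
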